8.3.6 ADVERSE EVENT REPORTING TIMEFRAMES

Adverse device or drug effects, including an unanticipated adverse device effect (UADE) or serious adverse event (SAEs) shall be reported to the Sponsor within 24 hours of knowledge of the event. All UADEs or SAEs shall be reported to the IRB either per site IRB regulations, or at a minimum, no later than 5 days after knowledge of the event.

8.3.7 REPORTING ADVERSE EVENTS TO STUDY PARTICIPANTS

Reportable events shall be reviewed and summarized in a timely manner. A report of these events shall be provided to the study investigators and shared with study participants at the investigator's discretion.

8.3.8 REPORTS OF SPECIAL INTEREST

In this study, hypoglycemia should not be reported as an adverse event unless it is designated as a Serious Adverse Event (See Section 8.3.2). Hypoglycemic events will be collected and categorized according to American Diabetes Association criteria as follows:

- Level 1: Glucose value \leq 70 mg/dL
- Level 2: Glucose value $<$ 54 mg/dL
- Level 3: Severe hypoglycemia associated with cognitive impairment requiring external assistance for recovery

Level 3 hypoglycemia episodes should be reported as a serious adverse event per section 8.3.2.

Hypoglycemia data will be collected from SMBG meter uploads, CGM data and participant diaries.

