2.3.3 RISK BENEFIT ANALYSIS

This study includes T1DM participants who undergo routine diabetes treatment and glucose control methodology. A standardized study protocol, case report forms, study and investigational device use training will be provided to all study investigators/staff and study participants prior to any study related intervention or testing.

The study population consists of adult volunteer participants who have been diagnosed with T1DM, and have used an insulin pump for at least 6 months for basal and bolus insulin therapy to control their blood glucose. T1DM diagnosis will be confirmed at screening by c-peptide lab test.

Only insulin pump users with at least 6 months of experience with pump therapy will be enrolled to minimize the risk of pump use errors. Each potential study participant will be required to submit a minimum of 14 days of pump data to confirm pump use compliance. Patients who routinely wear their infusion set for > 4.5 days will be excluded from participation to ensure a homogenous patient population of participants who adhere to infusion set labeling restrictions. Screening including physical exam, ECG and laboratory testing will rule out patients with anemia or known cardiovascular disease who may be at greater risk of procedure-induced anemia or whose hypoglycemia symptoms may be masked by concomitant medication.

The primary risks associated with extended wear of the Achilles infusion set are increased risk of hyperglycemic or hypoglycemic episodes and/or infusion site irritation or infection. To ensure patient safety while using the newly developed infusion sets, patients are required to wear a CGM sensor throughout the study. Only patients with at least 3 months of CGM experience will be recruited. The personal CGM should be set with alarm systems engaged throughout study duration. Study staff will be able to monitor each patient's interstitial glucose remotely and will be notified via text in case of alarm. Participants will be instructed to contact their study site for any issues.

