6.4 STUDY COMPLIANCE

Study compliance will be assessed during the initial participant instruction period, and by review of daily diary and Dexcom G6 app entries. The investigational device will be applied to the study participant only after the participant has demonstrated an understanding of the study instructions, change out activities, the need to complete all study test requirements as written. If the study staff become aware of participant non-compliance to protocol requirements or follow-up evaluations, multiple attempts will be made to contact the participant to ensure patient safety and protocol adherence.

Adherence to glucose test procedure will be assessed by study personnel at site. All CRFs must be completed and CGM data will serve as electronic source documentation for hyperglycemic and hypoglycemic adverse events. Additionally, inquiries documented in clinic notes will be used for source documentation of patient-reported AEs. Photographs of infusion site will serve as source documentation for infusion site reactions.

The following will be collected regularly and documented:

- Study participant's insulin pump records
- Interstitial fluid glucose data from Dexcom G6® CGM throughout each study period (assessed by study staff at each study visit)
- BG measurements per Bayer Contour NEXT device will be used by participants for SMBG data collection as mandated by protocol requirements. Data will be downloaded at each clinic visit
- Serum ketones - measured by Abbott Precision Xtra Ketone meter (in case of hyperglycemia occurring during fasting or acute illness)
- Study participant diary (Pain score, SMBG)

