4.3.2.6 Continues Glucose Monitor (CGM) Blood Glucose (BG)

Blood glucose concentration is captured in a commercial CGM device and the data is exported into a csv or excel file and imported into SAS.

- CGM is coming from two sources: Dexcom CGM and Medtronic CGM using by some automatic Pump.
- The data from Dexcom CGM will be used for analyses, only if there are missing data in Dexcom CGM, the data from Medtronic Pump CGM will be used for substitution.

The mean daily CGM glucose, standard deviation (SD) of daily CGM glucose and time (%) spent in glucose range of daily CGM glucose will be summarized.

All CGM parameters will be based on out-patient days' data only.

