4.4.5.4 Device Malfunctions

Device malfunctions as specified in section 4.3.3.1 will be presented descriptively

Population	Safety
------------	--------

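### Level 1 and 2 hypoglycemia, part of a named primary risk of the device, is collected but kept out of AE reporting, and the SAP text defines no event count for it

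*Protocol*

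**What the plan says.** Protocol 2.3.3 states: "The primary risks associated with extended wear of the Achilles infusion set are increased risk of hyperglycemic or hypoglycemic episodes", and adds site irritation or infection.

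Protocol 8.3.8 then sets the reporting rule: "hypoglycemia should not be reported as an adverse event unless it is designated as a Serious Adverse Event". In its place, "Hypoglycemic events will be collected and categorized according to American Diabetes Association criteria as follows": Level 1 at ≤70 mg/dL, Level 2 at <54 mg/dL, and Level 3 for severe episodes with cognitive impairment needing outside help. The sources are SMBG uploads, CGM and diaries. For the top level, "Level 3 hypoglycemia episodes should be reported as a serious adverse event per section 8.3.2".

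The safety endpoints in the Protocol synopsis and the safety analyses in Protocol 9.4.4 do not mention hypoglycemia. SAP 4.3.3 and 4.4.5 cover device malfunctions, VAS pain, exposure, AEs, ECG and vital signs. On malfunctions, SAP 4.4.5.4 says: "Device malfunctions as specified in section 4.3.3.1 will be presented descriptively". That list includes two kinds of hyperglycemia and no hypoglycemia.

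SAP 4.3.2.6.4 defines the percentage of CGM readings <54 and <70 mg/dL, as an efficacy variable. SAP 4.3.2.6 restricts it: "All CGM parameters will be based on out-patient days". SAP 4.4.4.2.4 summarizes it descriptively in the ITT population, and SAP 4.4.2 splits descriptive summaries by treatment and period.

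**The concern.** Keeping frequent, non-serious lows off the AE form is reasonable if they are tabulated somewhere else. Protocol 8.3.8 appears to intend that, since it sets up a three-level classification. But the classification feeds nothing: no later section of the protocol or SAP takes up Levels 1 and 2.

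Followed exactly, the plan gives safety tables in which hyperglycemia is counted under two definitions while hypoglycemia appears only if it is serious. SAP 2.5 records that the study was stopped after the seventh completer. In a study of that size, severe events may be too few to inform, so Level 1 and 2 counts by device would carry most of the available event information on this risk.

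**Working it through.** No figure in the plan needs reproducing. The check follows each level from collection to output.

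| Level | AE reporting (Protocol 8.3.8) | SAP safety output (4.3.3, 4.4.5) | Related SAP efficacy output |
|---|---|---|---|
| 1 (≤70 mg/dL) | Not an AE unless serious | None defined | % CGM readings <70 |
| 2 (<54 mg/dL) | Not an AE unless serious | None defined | % CGM readings <54 |
| 3 (severe) | SAE | AE summary or listing (4.4.5.1) | None specific |

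For comparison, SAP 4.3.3.1 counts hyperglycemia above 250 mg/dL that does not respond to a correction bolus, and hyperglycemia above 250 mg/dL with ketones ≥0.6 mmol/L.

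Can the CGM percentages stand in for an event count?

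1. **Unit.** The variable is readings below the cut divided by all available readings. The same percentage can come from one long low or several short ones, so neither the number of events nor the number of participants with an event can be recovered from it.
2. **Sources.** Protocol 8.3.8 names three sources. The SAP variable uses CGM only, so a low seen only on the meter or in the diary is lost.
3. **Days covered.** Clamps fall on days 0, 3, 5 and 7 (Protocol 1.3), and participants come in the evening before each (Protocol 6.1.1.4). SAP 4.3.2.6.1 works in calendar days with at least 276 of 288 readings after interpolation. The SAP does not define an out-patient day. If it means any day without a clamp, days 1, 2, 4 and 6 can qualify: 8 − 4 = 4 of the 8 wear days. If it means a day spent wholly outside the clinic, days 2, 4 and 6 also drop out because they end in clinic: 4 − 3 = 1 of 8, namely day 1. The protocol synopsis defines the CGM endpoints from day of insertion through day 7 inclusive.
4. **Population.** The CGM summary is on ITT, which requires eligibility, randomization and at least one completed clamp. The Safety population requires only that a cannula was placed. A participant with a set inserted but no completed clamp is in the second and not the first.
5. **Cut-off.** The protocol uses ≤70 mg/dL, both for Level 1 and for its CGM endpoint. The SAP uses <70. A reading of exactly 70 is counted under one and not the other.

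The CGM summary is therefore a related measure with partial coverage. It is not a tabulation of the events that Protocol 8.3.8 says will be categorized.

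**The case against.** The strongest reply is that hypoglycemia is not missing from the plan. Level 3 events, and any others meeting the seriousness criteria of Protocol 8.3.2, reach the AE output in the Safety population. CGM time in the low ranges is summarized by treatment, and Protocol 9.4.8 adds per-patient listings of secondary endpoints, so an excess of lows with one device could show. Calling that output efficacy does not hide it. All of this stands. A reader might infer that the trial cannot report on hypoglycemia at all; the documents do not support that.

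Other stronger readings also fail:

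- **Stopping circumstances.** One might think that the severe-hypoglycemia circumstance in Protocol 10.1.1.3 is left without data. It turns on three or more participants with severe events, and Level 3 reporting is mandatory.
- **Protocol 6.4.** It says that "CGM data will serve as electronic source documentation for hyperglycemic and hypoglycemic adverse events", which may look like a contradiction of 8.3.8. It can be read consistently, because serious hypoglycemia is still an adverse event.
- **Clinic sessions.** One might multiply eight clamps by seven completers and call that the amount of glucose data left out. The product is only a ceiling, because a set change ends that period's clamps (Protocol 6.1.1.8). The overnight stay before day 0 precedes set insertion (Protocol 6.1.1.5). Overnight IV insulin is discretionary, and glucose during clamps is held at target by titrated dextrose. Lows there say little about the device, so leaving them out of the device comparison is defensible.
- **Table list.** SAP 6 refers to an attached file that is not among the supplied documents. A hypoglycemia listing there cannot be excluded, although the SAP text defines no variable from which to build one.

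None of these replies supplies a count of Level 1 or 2 events.

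**Conclusion.** The point holds for non-serious Level 1 and 2 events. They are part of a named primary risk, a stated rule takes them out of AE reporting, they are collected and categorized, and the supplied text then specifies no event count, participant count or table by device. Hyperglycemia has two counted safety variables and hypoglycemia has none. What remains is a partial CGM percentage covering, on the two readings of an out-patient day above, between one and four of eight wear days, with a cut that differs from the protocol's.

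The size is modest: a reporting gap that should be closed, with no bearing on the primary analysis. The conclusion rests on the protocol and SAP text as supplied, and assumes that the unseen table list does not fill the gap.

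**What to change.** In SAP 4.3.3, add a hypoglycemia variable with a stated rule for what counts as one episode. The rule should say how SMBG, CGM and diary records of the same low are combined, and whether a Level 2 event is also counted at Level 1, since the protocol's limits overlap as written.

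In SAP 4.4.5, for the Safety population, add a descriptive table for home wear at each protocol level, by device and period: participants with at least one event, number of events, and rate per wear-day. List lows during overnight stays or clamps separately as procedure-related, and do not attribute those before set insertion on day 0 to the device. Change the SAP cut from <70 to the protocol's ≤70 mg/dL.

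The cost is one definition and one or two tables, with no new data collection. The downside is limited information: with seven completers the counts may be small, and the table should be read as description, not as a test between devices.

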8.3.9 REPORTING OF PREGNANCY

Female participants who become pregnant during the intervention or testing period shall return to the investigational site for a physical exam to ensure safety. Upon potential or confirmed pregnancy, female participant shall be exited from the study and no further testing or evaluations will be made, UNLESS participant is experiencing an adverse event. If participant is experiencing an adverse event related to study intervention or testing, the AE should be reported as above in Section 8.3.5 and participant should be followed until resolution or stabilization of the event.

8.4 UNANTICIPATED PROBLEMS

This study is considered to be a low risk device evaluation. However, if an Investigator or Sponsor become aware of an issue that is "Unexpected in terms of nature, severity, or frequency, or related or possibly related to participation in the research or puts the research participants or others at a greater risk of harm (including physical, psychological, economic, or social harm) than was previously known or recognized", these events shall be reported to the Sponsor and governing IRB within 24 hours of knowledge of the event(s).

8.4.1 UNANTICIPATED ISSUE REPORTING TO IRB

See Section 8.3 above.

8.4.2 UNANTICIPATED ISSUE REPORTING TO PARTICIPANTS

See Section 8.3 above.

9 STATISTICAL CONSIDERATIONS

A formal Statistical Analysis Plan (SAP) will be completed prior to database lock and un-blinding of the study data. The SAP generally includes additional statistical analysis detail (e.g., calculation of derived variables, data exclusion rules, listings of tables, figures and listings produced, etc.).

9.1 STATISTICAL HYPOTHESES

- Null Hypothesis: There is no difference in the population mean rates of decline for the Achilles and control infusion sets, as measured by the slope (s) contrast for the $\ln(\text{AUC}_{0-300(\text{GIR})})$ assessed over study days DOI, day 3, day 5, and day 7.
- Alternative Hypothesis: The rate of decline (slope coefficient s) for the Achilles infusion set is less than the corresponding rate for control

9.2 SAMPLE SIZE DETERMINATION

A sample size of 24 participants is sufficient to generate 90% power for a 2-tailed $p=0.05$ comparison of the $\ln(\text{AUC}_{0-300(\text{GIR})})$ slope contrasts (=control minus Achilles), within this 2x2 crossover design. In addition to the usual regularity assumptions for the 2x2 crossover design (i.e. no carryover effects), this computation was based on the following assumptions:

1. The $\ln(\text{AUC}_{0-300(\text{GIR})})$'s are normally distributed.
2. The within participant variance is 40% of the total variance.
3. The study day correlation matrix of the within-participant $\ln(\text{AUC}_{0-300(\text{GIR})})$ assessments is AR(autoressive model) with correlation $r=0.5$.
4. The within plus among participant variance for the $\ln(\text{AUC}_{0-300(\text{GIR})})$'s is 0.21 (based on previous studies).
5. The difference in slopes (Achilles minus control) is at least 0.07.

9.3 POPULATIONS FOR ANALYSES

Intention-to-Treat (ITT) Analysis Population: all patients that meet all inclusion criteria and none of the exclusion criteria and are randomized to treatment sequence and complete at least one glucose clamp procedure will be included in the ITT population.

Safety Analysis Population: all patients who had either an investigational or control cannula implanted.

Per-Protocol (PP) Analysis Population: all patients who completed both treatment sequences with no major protocol violations.

The primary effectiveness analysis will be based on the ITT participant population. Sensitivity analyses of the primary effectiveness endpoint will be generated based on the PP population. The ITT population may contain some patients that complete the first treatment, but not the second, and vice versa. This will require the use of imputation methods for missing values, which are documented in Section 9.4.2.

The primary safety analysis will be based on the Safety population. All secondary and exploratory effectiveness analyses will use the PP population.

9.4 STATISTICAL ANALYSES

9.4.1 GENERAL APPROACH

As a routine evaluation of the data during analysis, consistency of the study variables to properties of statistical tests will be checked. The parameter for the primary analysis will be log-transformed, and the rest of the PK as well as PD parameters will be log-transformed as appropriate before analysis. With categorical data, exact statistical test procedures will be used to minimize test assumptions, except when Wilson Score confidence intervals can be calculated.

All data will be tested for normality using the Shapiro-Wilk test. Data that is highly skewed or contains outliers even after the log transformation will be analyzed using the rank transformation, namely analyzing the ranks of the assessments within the combined sample. The paired measurements will be analyzed with dependent *t* tests or Wilcoxon signed rank tests, as indicated. AUC data will be calculated with the trapezoidal rule for defined PK/PD time points. Post hoc analyses will be performed after confirmation of significant main effects. Unless otherwise specified, data will be reported as mean \pm SD with $p < 0.05$ considered statistically significant.

A data convention used in this analysis is as follows: for tabulated continuous variables, the descriptive analyses will present the mean, standard deviation, median, minimum and maximum. And for tabulated categorical variables, the number with the characteristic, the total number evaluated, the percent and the 95% Wilson Score confidence intervals will be provided.

For secondary endpoint analyses, two-tailed significance tests will be performed with significance level $p = 0.05$.

For the estimation of catheter failures, we used data from the study of Patel *et al.* who investigated steel and Teflon infusion sets worn over a 7-day period.⁵ They reported that 42% of participants could consistently wear an infusion set for 6-7 days (58% failure) without a deterioration in glucose levels. It should be noted that their failure rate also included accidental removal of catheters, removal due to pain, and removal due to poor adhesion of catheter pad (total 32%). Since our participants will be in a more controlled setting (i.e. clinical research staff will be inserting and carefully securing the devices

using an aseptic technique), we anticipate having lower failure rates related to early catheter removal. We therefore assume a 40-50% failure rate to be a reasonable estimate of total anticipated failures and have added 6 additional participants for an anticipated total sample size of n=30. (Statistical analyses were performed using Systat version 13.)

9.4.2 ANALYSIS OF THE PRIMARY EFFICACY ENDPOINT(S)

The $\ln(\text{AUC}_{0-300(\text{GIR})})$ on DOI (day 0) and days 3, 5, 7, periods 1 and 2 will be calculated using the trapezoidal rule. A mixed-effects (repeated-measures) linear model with treatment and period as fixed effects and participant as a random effect will then be fit to this data. Estimates of the slopes by treatment will be generated as contrasts based on the least squares means. Treatment comparisons and confidence bounds on the difference in slopes will be presented. Details will be provided in the Statistical Analysis Plan

The natural log of each AUC mean slopes for the two treatment groups will be compared in a mixed-effects (repeated-measures) linear model with treatment and period as fixed effects and participant as a random effect.

The primary analysis will be conducted on the ITT population; the mixed-effects model accounts for missing data using a missing at random (MAR) assumption, which will be checked.

9.4.3 ANALYSIS OF THE SECONDARY ENDPOINT(S)

Secondary analyses will use the both ITT and PP populations for analysis.

The survival of the Achilles and control infusion sets will be compared using a discrete lifetable analysis over study days 0, 3, 5, and 7 and the discrete form of the log-rank test.

All pharmacokinetic parameters (AUCs , t_{50} , C_{max} , t_{max} , MRT for the insulin concentration by time curve, etc.) will be estimated using non-compartmental models and log-transformed before analysis. Means for the two treatment groups will be compared in a mixed-effects (repeated-measures) linear model with treatment and period as fixed effects and participant as a random effect. The mean difference between treatments (on the log-scale) will be compared with a two-sided test using significance level $\alpha=0.05$. Then mean ratio and its 95% confidence interval will be calculated by inverse-transforming the mean difference and its 95% confidence interval.

All pharmacodynamic parameters (AUCs , onset time and time to return to baseline for the glucose concentration by time curve, etc.) will be estimated using non-compartmental models. Means for the two treatment groups will be compared in a mixed-effects (repeated-measures) linear model with treatment and period as fixed effects and participant as a random effect. The mean difference between treatments will be compared with a two-sided test using significance level $\alpha=0.05$. Wilcoxon signed rank tests will be used if the data is significantly skewed.

9.4.4 SAFETY ANALYSES

Tolerability of infusion sets will be assessed by comparing the mean VAS scores from day of insertion through Day 7 of use with a mixed-effects (repeated-measures) linear model with treatment, period and day as fixed effects and participant as a random effect. The mean difference between treatments will be compared with a two-sided test using significance level $\alpha=0.05$.

Adverse events (AEs) will be coded using CTCAE v4.0. Descriptive statistics (number of participants and per-participant incidence) for device-related AEs will be presented by System Organ Class, Preferred term, severity and treatment. Unanticipated and serious device-related AEs will be presented separately by treatment.

